8.3.3. Exploratory Endpoints

8.4. AE ANALYSIS

All subjects who have IP applied at least once will be included in the safety analysis. All AEs reported during the AE reporting period will be listed by subject number. The number of subjects experiencing AEs will be presented by body system, preferred term, and treatment (if assessed as related to a particular IP). The latest version of the Medical Dictionary for Regulatory Activities (MedDRA) will be used as the adverse event classification system.

Version & Date: Amendment 3: Final Version 4.0, 28 Aug 2019

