1. INTRODUCTION

The primary goal in wound care is to protect the wound from further damage and to facilitate healing by providing the optimal environment that limits infection, inflammation and scarring. Appropriate wound dressings play an important role in providing this necessary protection and may promote restoration of skin barrier function compared to untreated wounds.¹

Wound healing is a complex process wherein the skin surface and the underlying tissue must go through an intricate process of tissue repair. The dermis of an uncovered wound is relatively more fibroplastic, fibrotic, and scarred compared to occluded wounds, and is likely to be more inflamed and necrotic in early stages of repair. Exudate, the moisture secretion from the wound site, facilitates the healing process, by providing a variety of bioactive mediators such as enzymes, growth factors and hormones. Wound exudate may also aid in limiting inflammation by providing various immune cells with an ideal medium to destroy invading pathogens such as bacteria, foreign bodies and necrotic tissues. However, exudate in an uncovered wound can lead to scab formation, with trapped inflammatory cells, wound debris, and a layer of desiccated dermal tissue. Covering a wound with an occlusive dressing reduces scab formation and may radically alter the pattern of epidermal wound healing.

Another factor that plays an important role in wound healing is the moisture in the wound environment. As early as 1962, Winter et al., provided the first evidence that keeping wounds moist helps them heal faster compared to dry wounds.²

As occlusion affects both the epidermis by enhancing epithelial cell migration and the dermis by enhancing dermal collagen synthesis, maintaining a moist environment may promote the restoration of epidermal barrier function and overall wound healing while making dressing changes relatively easier. Moreover, it has been suggested that the scar left by an occlusively dressed wound is more cosmetically acceptable than that left by an uncovered wound.³

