6.1. IDENTITY OF INVESTIGATIONAL STUDY MATERIALS

The following IPs and auxiliary product will be provided under authorization of the Sponsor:

Table 1. IP and Auxiliary Product List/Study Treatments

Treatment Code/Identification	UPC/PR#	Product type	Regulatory Class in USA
		N/A - uncovered wound; Negative Control	N/A
		IP —	
"Bandage"		IP – Benchmark Control 1	
A – H		IP – Benchmark Control 2	
(as randomly assigned		IP	
by Sponsor)		IP	
		IP	
		IP	
		Auxiliary Product	Cosmetic

A letter of non-significant risk, which outlines the safety of the IPs, will be provided to the IRB and the PI and filed in the SMF.

The Ingredient List for the auxiliary product is provided in Appendix IV.

All the investigational study materials will be manufactured according to Good Manufacturing Practices.

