6.5.2. IPs

All IP application and removal will be performed at the study site as described below by trained study staff wearing gloves and according to the randomization schedule (see section 6.6).

[figure not shown]

is for single use; used bandages will not be re-applied and should be discarded by the Site as described in section 6.3.

IP will be applied by a designated study staff member as follows:

Version & Date: Amendment 3: Final Version 4.0, 28 Aug 2019

Different Adhesive Bandages Protocol Number: CCSTOH001689

[figure not shown]
Version & Date: Amendment 3: Final Version 4.0, 28 Aug 2019

Additional application details for all IPs:

- If a wound shows signs of excessive redness, pain, or swelling or signs of infection (which should be documented as an AE, per section 10.3.2.1), IP will not be applied.
- Subjects will also be provided a roll of tape to take home for use in case IPs
- If an IP falls off at home, subjects will be instructed to report the date and time that the IP fell off and report that information at their next visit. IPs will not be replaced at home if they fall off. Subjects will be instructed to retain any IPs that have fallen off and bring them to their next appointment.
- them to their next appointment.

IP will be removed by a designated study staff member as follows:

become loose between clinic visits.

Version & Date: Amendment 3: Final Version 4.0, 28 Aug 2019

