7.2.5.2. IP Application

After completion of the clinical grading and instrumental evaluations, IPs will be applied to the randomly assigned test sites, as described in section 6. The untreated test site will remain uncovered.

Subjects will be reminded of the study instructions (Appendix III).

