6.5 SAFETY ANALYSIS

All subjects who have IP applied at least once will be included in the safety analysis. All AEs reported during the AE reporting period will be listed by subject number.

The number and percentage of subjects experiencing treatment-emergent adverse events will be presented by body system and preferred term. Treatment-emergent adverse events are those with a start date and time on or after the date and time of first use of investigational product, or the AEs started before the first use of investigational product and worsened after it. The latest version of the Medical Dictionary for Regulatory Activities (MedDRA) will be used as the adverse event classification system.

Number and percentage of subjects with serious adverse events will be summarized by MedDRA system organ class and preferred term.

Number and percentage of subjects with treatment-related adverse events will be summarized by MedDRA system organ class and preferred term. Treatment-related AEs are events evaluated by the investigator as possible, probable or very likely related to

Protocol CCSTOH001689
Statistical Analysis Plan

investigational product. AEs with unknown relationship to treatment will be considered as treatment-related.

APPENDICES

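### Protocol 8.4 cannot show a local adverse event at the uncovered site under its own treatment, and the SAP's adverse event tables have no treatment split at all

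*Protocol*

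**What the plan says.** Protocol 8.4 gives an AE a treatment label only on a condition. Subjects with AEs are presented by body system, "preferred term, and treatment (if assessed as related to a particular IP"). The same section keeps a full listing: "All AEs reported during the AE reporting period will be listed by subject number".

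Protocol Table 1 (section 6.1) labels seven of the eight treatments as IPs. The eighth is "N/A - uncovered wound; Negative Control". Section 7.2.5.2 confirms that it receives nothing: "The untreated test site will remain uncovered".

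SAP 6.5 has no treatment dimension: "The number and percentage of subjects experiencing treatment-emergent adverse events will be presented by body system and preferred term". Serious and treatment-related AEs are summarised the same way, and the titles of Tables 14.3.1 to 14.3.3 match. Relatedness is defined against the product: "Treatment-related AEs are events evaluated by the investigator as possible, probable or very likely related to" investigational product, with unknown relationships counted as related. Protocol 10.3.2.4, by contrast, grades causality against participation in the study.

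The plan expects local AEs. Protocol 6.5.2 covers wounds with excessive redness, pain or swelling, or with "signs of infection (which should be documented as an AE, per section 10.3.2.1), IP will not be applied".

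**The concern.** The treatments are randomised to wound sites within each subject, so a by-treatment safety display has to work at site level. The only by-treatment AE display in either document passes through a relatedness filter that one of the eight treatments cannot pass. An infection at a bandaged site can be attributed to that bandage and shown against it. The same infection at the uncovered site has no product to be attributed to.

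The Introduction describes the aim of wound care as to "facilitate healing by providing the optimal environment that limits infection, inflammation and scarring", and describes uncovered wounds as likely to be more inflamed early in repair. If bandages do reduce local AEs, this display could not show it. Someone reading its columns against an absent or empty control entry could conclude that only bandaged wounds had problems.

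**Working it through.** The plan states no AE rate and no AE comparison, so there is no figure of its own to reproduce. The check is textual, followed by an illustration in which every rate is an assumption.

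**1. Can any planned AE output compare the eight treatments?**
- Protocol 8.4 by-treatment display: requires relation to a particular IP, so the uncovered site is excluded. If a control-site event were attributed to a neighbouring bandage, it would appear under that bandage.
- Protocol 8.4 and SAP 6.5 counts by class and term: these include control-site events. They count subjects, and every subject has all eight treatments, so they cannot separate one treatment from another.
- AE listings: these contain every event but are not a summary by treatment.
- Graded and self-assessed measures (SAP 6.3): the IPs are compared with the negative control on erythema, edema, TEWL, scar score, pain and itch. Infection is not graded, and pain and itch are collected only to Day 4.

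No planned summary covers discrete local AEs for all eight treatments.

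**2. How many events could go unlabelled?** Let p0 be the risk of a local AE at the uncovered site (assumed). Each subject has one such site. The expected number is n × p0, and the chance of at least one is 1 − (1 − p0)^n, treating subjects as independent. The values of n are the protocol's 40 enrolled and 30 completing.

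| p0 | n = 40: expected | n = 40: at least one | n = 30: expected | n = 30: at least one |
|---|---|---|---|---|
| 2.5% | 1.0 | 63.7% | 0.75 | 53.2% |
| 5% | 2.0 | 87.1% | 1.5 | 78.5% |
| 10% | 4.0 | 98.5% | 3.0 | 95.8% |

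As a share of all site-local AEs, with r the uncovered-site rate divided by the average bandaged-site rate, the unlabelled part is r/(r + 7):
- r = 0.5: 0.5/7.5 = 6.7%
- r = 1: 1/8 = 12.5%
- r = 2: 2/9 = 22.2%

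**3. Which way would a reader be misled?** Let p1 be the true risk at a bandaged site, f the share of background AEs there that are attributed to the IP, and s the share of bandage-caused AEs so attributed. If the control is read as zero:

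displayed difference = f × min(p0, p1) + s × max(p1 − p0, 0) − 0

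| p0 | p1 | f | s | True difference | Displayed | Error (points) |
|---|---|---|---|---|---|---|
| 5% | 5% | 0 | 1 | 0 | 0 | 0 |
| 5% | 5% | 1 | 1 | 0 | +5 | +5 |
| 5% | 10% | 0 | 1 | +5 | +5 | 0 |
| 5% | 10% | 1 | 1 | +5 | +10 | +5 |
| 5% | 10% | 0 | 0.5 | +5 | +2.5 | −2.5 |
| 10% | 5% | 0 | 1 | −5 | 0 | +5 |
| 10% | 5% | 1 | 1 | −5 | +5 | +10 |

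When p1 ≥ p0 the error can be zero, positive or negative, depending on attribution. When p1 < p0 the display equals f × p1, which cannot fall below zero. The error is then f × p1 + (p0 − p1), which is at least p0 − p1 whatever the attribution.

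**The case against.** The case on the other side has four parts, and most of it stands.

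First, nothing is lost from the record. A control-site infection is listed, and if it starts after first IP use it enters the treatment-emergent table. It can also be reported as study-related, because protocol causality refers to the study. A reader might infer that harms at the uncovered site are counted as zero in the trial. The documents do not support that: only the treatment label is unavailable. Protocol 8.4 does not say that a control column would be printed, and the entry may simply be absent.

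Second, no bandage-versus-uncovered AE comparison or AE hypothesis is planned, and the SAP drops the split. There is therefore no planned estimate to be biased.

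Third, a reader might infer that the rule works against every bandage. It need not. The same filter removes unattributed events from the bandage columns, so the error can be zero or can favour a bandage. A full reversal of order, such as 4 true events at the uncovered site and 2 at a bandage displayed as 0 and 2, needs the assumed 10% and 5% risks, 40 subjects and every bandage-site event judged related.

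Fourth, local redness, swelling, pain and itch are already compared with the control regardless of causality. That narrows the gap, but it leaves infection and other discrete AEs, and pain or itch after Day 4, uncovered.

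The objection does not remove two facts: the one by-treatment AE display excludes a randomised treatment, and subject-level tables cannot stand in for it.

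**Conclusion.** The point holds as a reporting gap that is cheap to close; it does not affect the primary analysis. By the documents' own definitions, a local AE at the uncovered site cannot be shown under its treatment in Protocol 8.4, and a protective effect of a bandage on local AEs cannot be displayed there under any attribution. The SAP removes the split instead of repairing it, so the two documents disagree and neither summarises local AEs over all eight treatments.

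The structural part rests on Table 1 and section 8.4 alone. The size rests on assumed rates: 1 to 4 expected unlabelled control-site events in 40 subjects for risks of 2.5% to 10%, or 6.7% to 22.2% of site-local AEs for r from 0.5 to 2. Apart from the protective case, the direction of any distortion is not determined by the plan.

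**What to change.** Align Protocol 8.4 and SAP 6.5 on whether and how AEs are shown by treatment. Then:
- Add one descriptive table of AEs localised to a wound site, by the treatment assigned to that site, for all eight treatments including the uncovered control and regardless of assessed relationship. Use wounds per treatment as the denominator. Each subject contributes one wound to each treatment, so the denominators are equal by design.
- Make sure the test-site number (1 to 8) is captured with each local AE. The AE form is not among the documents, so this may already be done. If it is not, it should be added prospectively, because the site may be hard to recover later.
- Keep the IP-related summary as a separate table, with a note that the uncovered control cannot contribute to it.

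The cost is wording in two sections, one table and at most one data field, with no added visits or subjects. Counts per treatment will be small, so the table is descriptive only and should carry no tests.

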9. SUCCESS CRITERIA

10. MANAGEMENT OF INTERCURRENT EVENTS

10.1. AMENDMENTS TO THE PROTOCOL

Neither the PI/Site nor the Sponsor will modify this protocol without obtaining the agreement of the other.

Amendments must be approved by the Sponsor and the IRB/IEC prior to implementation.

The only circumstance in which an amendment may be initiated prior to IRB/IEC approval is where the change is necessary to eliminate apparent immediate hazards to the subjects. In that event, the PI must notify the IRB/IEC and the Sponsor in writing within 3 working days after the implementation.

10.2. PROTOCOL DEVIATIONS

Protocol deviations should be avoided whenever possible. When a protocol deviation occurs, it must be captured on the Protocol Deviation Log (or equivalent).

If a significant deviation occurs, the PI or designee will also contact the SM (see contact information on front page or in Appendix VII). Contact with the SM will be made as soon as possible in order to discuss the situation and agree on an appropriate action. If it is determined that a subject's safety/well-being was affected, the IRB/IEC will also be notified, as applicable. The final study report will describe any deviation from the protocol and the circumstances requiring it.

10.3. ADVERSE EVENT REPORTING

10.3.1. Introduction

Timely, accurate, and complete reporting and analysis of safety information from clinical studies are crucial for the protection of subjects, investigators, and the Sponsor, and are mandated by regulatory agencies worldwide. The Sponsor has established procedures in conformity with regulatory requirements to ensure appropriate reporting of safety information.

10.3.2. Definitions

10.3.2.1. Adverse Event (AE)

An AE is any untoward medical occurrence in a clinical study subject temporally associated with the clinical investigation, whether or not the event has a causal relationship to the subject's participation in the trial. It is therefore any unfavorable and unintended sign (including an abnormal finding), symptom, or disease that occurs during the trial. This can include any occurrence that is new in onset, an aggravation of

Different Adhesive Bandages Protocol Number: CCSTOH001689

Version & Date: Amendment 3: Final Version 4.0, 28 Aug 2019

severity/frequency of a baseline condition, or abnormal results of diagnostic procedures, including laboratory test abnormalities.

Examples of AEs include but are not limited to:

- Abnormal test findings,
- Clinically important symptoms and signs,
- Changes in physical examination findings,
- Hypersensitivity, and
- Progression/worsening of underlying disease.

Any change in existing medical condition (medical history) may be considered an AE and recorded appropriately.

Additionally, they may include the signs or symptoms resulting from:

- Product overdose,
- Product withdrawal,
- Product abuse,
- Product misuse,
- Product interactions,
- Medication errors,
- Product dependency,
- Exposure in utero (EIU), and
- Study related procedures.

The criteria for determining whether an abnormal objective test finding should be reported as an AE are as follows:

- Test result is associated with accompanying symptoms, and/or
- Test result requires additional diagnostic testing or medical/surgical intervention, and/or
- Test result leads to a discontinuation from the study, significant additional concomitant treatment, or other therapy, and/or
- Test result is considered to be an AE by the Study Physician or the Sponsor.

Merely repeating an abnormal test, in the absence of any of the above conditions, does not constitute an AE. Any abnormal test result that is determined to be an error does not require reporting as an AE.

Expected Events

Expected mild reactions (e.g. bleeding, pain, itching, etc.) related to the laser wounding procedure, normal healing process, and IP removal will not be captured as AEs unless there is exacerbation (moderate or severe) of these reactions as judged by the PI or designee. All reactions will be documented in the source documents.

Pre-Treatment AE (PTAE)

A PTAE is defined as any AE present prior to the initiation of the treatment/administration of IP.

Different Adhesive Bandages Protocol Number: CCSTOH001689

Version & Date: Amendment 3: Final Version 4.0, 28 Aug 2019

10.3.2.2. Serious Adverse Event (SAE)

An AE (untoward medical occurrence) will be considered an SAE if it meets either of the following definitions:

Definition 1:

The event fulfills at least one of the following criteria:

- Results in death
- Is life-threatening (immediate risk of death)
- Requires inpatient hospitalization or prolongation of existing hospitalization
- Results in a persistent or significant incapacity or substantial disruption of the ability to conduct normal life functions
- Is a congenital anomaly/birth defect
- Is considered a medically significant event (medical and scientific judgment should be exercised in deciding whether expedited reporting is appropriate in other situations, such as important medical events that may not result in death, be life-threatening, or require hospitalization but may be considered a serious adverse drug experience when, based upon appropriate medical judgment, they may jeopardize the patient or subject and may require medical or surgical intervention to prevent one of the other outcomes listed above. Examples of such medical events include allergic bronchospasm requiring intensive treatment in an emergency room or at home, blood dyscrasia, or convulsions that do not result in hospitalization; or development of drug dependency or drug abuse, or malignancy)
- Is a suspected transmission of any infectious agent via a product (medically significant)

Definition 2:

- the event involves subject contact with a device AND
- the event results in:
 - o Death
 - Serious injury, which means an injury or illness that:
 - Is life-threatening (immediate risk of death)
 - Results in permanent impairment of a body function or permanent damage to a body structure, or
 - Necessitates medical or surgical intervention to preclude permanent impairment of a body function or permanent damage to a body structure (permanent means irreversible impairment or damage to a body structure or function, excluding trivial impairment or damage).
 - Persistent or significant incapacity or substantial disruption of the ability to conduct normal life functions
 - A malfunction that the device (or similar device marketed by the same manufacturer or importer) would be likely to cause death or similar injury if the malfunction were to recur.
 - Any suspected transmission of any infectious agent via a product (medically significant).

10.3.2.3. Severity

The severity of all AEs must be assessed by the Study Physician.

Protocol Number: CCSTOH001689

Version & Date: Amendment 3: Final Version 4.0, 28 Aug 2019

The severity classifications are:

- **Severe** Extreme distress, causing significant impairment of functioning or incapacitation; interferes significantly with subject's usual function; prevents normal everyday activities.
- **Moderate** Sufficient discomfort is present to cause interference to some extent with subject's usual function or normal everyday activity.
- **Mild** Awareness of symptoms that are easily tolerated, causing minimal discomfort and not interfering with subject's usual function or normal everyday activities.

Note the distinction between the severity and the seriousness of an AE. A severe event is not necessarily a serious event. For example, a headache may be severe (interferes significantly with subject's usual function) but would not be classified as serious unless it met one of the criteria for SAEs, listed above.

10.3.2.4. Causality Assessment

An AE (serious or non-serious) is considered "study-related" if the causality assessment is possible, probable, or very likely. The Study Physician determines the causality by using the following definitions:

- Not related an AE that is not related to the participation in the study.
- **Doubtful** an AE for which an alternate explanation is more likely (e.g. concomitant drug), or the relationship in time suggests that a causal relationship is unlikely.
- Possible an AE that might be a result of participation in the study. An alternative explanation is
 inconclusive and the relationship in time is reasonable so a causal relationship cannot be
 excluded.
- **Probable** an AE that might be a result of participation in the study. The relationship in time is suggestive (e.g. confirmed by the challenge). An alternative explanation is less likely.
- **Very Likely** an AE that is listed as a possible adverse reaction and cannot be reasonably explained by an alternative explanation. The relationship in time is very suggestive (e.g. confirmed by dechallenge and rechallenge).

